## RESEARCH PLAN

### 1 Literature review

This study focuses on learning clinical skills in nursing education and compares the students' learning outcomes of Mixed Reality Learning, Video-Based Learning and Instructor-led training in Nasogastric Tube (NGT) insertion. Learning clinical skills during nursing studies is known to enhance students' clinical competence and confidence (Gregersen et al., 2021; Edward et al., 2017). Clinical skills in this context are defined as both technical and non-technical skills, such as correct technique of NGT insertion, aseptic technique, patient education and interaction. A literature review by Motta et al. 2021 found that although nasogastric tube insertion is considered a simple procedure, incorrect NGT insertion into the airways or trachea can cause serious complications for the patient. The wrong location can cause discomfort, delayed eating, as well as increase mortality and increase hospital stay. Other adverse events included sinusitis, nasopharyngeal discomfort, nasal septal erosion, pressure ulcer and nosebleeds upon removal. (Motta et al., 2021.) Previous studies have shown that effective training increase students' confidence in correctly performing the steps for NGT insertion, assessing proper placement, and understanding potential complications (Kaltenmeier et al., 2022; Bomo Zah, 2020; Darawad et al., 2015).

Nursing education needs new teaching methods and strategies that encourage students to actively apply their clinical skills (Handeland et al., 2021; Natarajan et al., 2022). Millennial nursing students, who have embraced virtual learning, acknowledge the significant impact of teaching technology on their attention, knowledge acquisition, critical thinking, and overall satisfaction (Natarajan et al., 2022). Utilizing digital health technologies in education is important. These technologies can enhance and support individual student learning experiences and needs and contribute to sustainable development (European Commission, 2018; Opetus-ja kulttuuriministeriö, 2023; Valtioneuvosto, 2022).

Mixed reality (MR) is a promising tool for teaching clinical nursing skills (Schoeb et al., 2020; Rochlen et al., 2022). MR connects the real world to the virtual world with the help of special devices such as MR glasses. MR provides visual and auditory information and sometimes also sound, haptics, taste, smell, etc. (Speicher et al., 2019.) The term Extended Reality (XR) is also used, which is to describe "all" forms of new realities. XR includes Mixed Reality (MR), Augmented Reality (AR) and Virtual Reality (VR) and their various subforms. (Rauschnabel et al., 2022.) MR glasses are used to successfully perform clinical nursing skills through virtual instructions (San Martin-Rodriguez et al., 2019; Kim et al., 2021). Integrating MR into training allows healthcare professionals and students to practice and improve their technical and non-technical skills, as well as making clinical nursing decisions in critical and constrained situations safely (Frost et al., 2020; Son et al., 2023; Wunder et al., 2020). MR is a promising technique and tool for education to teaching clinical skills because it produces similar learning outcomes as teacher guidance (Schoeb et al., 2020; Ryan et al., 2022). The use of MR glasses has not been studied in nursing students at the NGT insertion.

It has been found the students' new learning experiences with MR can influence their satisfaction with the learning environment and the subject matter, which can lead to an improvement in their learning outcomes. (Almufarreh, 2023). The use of MR can enhance students' motivation and interest in the

subject being studied, facilitate individual learning, and increase the sense of success (Stelter & Kim, 2023; Rochlen et al., 2022). Using MR fostered a better and longer-term absorption of students' knowledge (Kolecki et al. 2022) and students experienced more meaningful learning (Chen 2021).

Usability is theoretically defined as the degree to which the user experiences learnability, efficiency, and satisfaction when using technology system (Shultz et al. 2015). MR can compensate for the shortcomings in VR, such as motion sickness and dizziness caused by isolation from the outside world. Therefore, MR can be used for longer periods than VR. This finding implies that MR can be applied in clinical nursing as the technology advances to integrate virtual and real environments. (Kim et al., 2021.) MR systems usability evaluated in Schoeb study 40.2% of participants (N=57) reported MR glasses difficult to use, and 28.9% believed they could only use the system with the help of the director. In its usability MR glasses still have shortcomings such as short battery life, complex handling as well as the necessary fast, reliable internet connection. (Schoeb et al., 2020.) The challenges of using MR include the novelty and unfamiliarity of the technology for the instructors. In the future, the use of MR should stress the importance of preparation at both the individual and the organizational level, as well as providing technical support to facilitate immersive learning. (Son et al., 2023.) The problem of availability remains, as MR devices are not widely used, and their accessibility should be enhanced (Kolecki et al., 2022).

Educational institutions, students, and health professionals should actively participate in the development of digital health technology (HIMSS, 2021; World Health Organization, 2021) In addition, it would be relevant to assess the usability of Mixed Reality Learning and Video-Based Learning as a learning method in nursing education. Despite some existing research on the topic, MR technology is still novel at the educational level and the potential of MR as a learning method has not been fully explored, especially learning nursing skills in nursing education. Previous research also indicates the need for further investigation into MR use in nursing education.

## 2 Research objectives and hypothesis

The main objective of the study is to develop Mixed Reality and Video Based Learning interventions and evaluate the results of the interventions. The aim is to assess and compare the learning outcomes of nursing students in nasogastric tube insertion using Mixed Reality Learning, Video-Based Learning and Instructor-led training. The aim is also to assess and compare the MR technology and video usability and to describe students' experiences with MR technology and identify the factors that either facilitate or hinder the learning of nursing skills within an MR environment.

Phases:

1. Development of the intervention; The aim is to develop two interventions. Intervention one is Mixed Reality Learning where the first-year nursing students will use MR glasses and virtual instructions for inserting a nasogastric tube. Intervention two is Video-Based Learning where the first-year nursing students will use video-based learning (VBL) materials to follow the same NGT insertion process. This includes the design, development and testing of the intervention.
2. Evaluation of the intervention; The aim is to assess and compare how different learning methods (Mixed Reality Learning, Video-Based Learning, and Instructor-led training) affect students' learning outcomes in NGT insertion. The study will also compare the usability of MR and video technology and describe students' experiences with MR technology.

The research hypothesis is that Mixed Reality learning (MR) and Video-Based learning (VBL) will both lead to better learning outcomes for first-year nursing students in nasogastric tube (NGT) insertion and clinical skills learning compared to traditional Instructor-led training. The expectation is that MR learning will produce the highest usability scores and most positive learning experiences.

### 3 Research implementation

The study will be conducted as a randomized controlled trial (RCT) with first-year nursing students in one University of Applied Sciences. In the first phase, the aim is to develop a Mixed Reality and Video- Based intervention utilizing the Medical Research Council (MRC) Framework. The MRC Framework serves as a guide for researchers in designing research projects and aids in the development and evaluation of complex interventions.

The MRC framework 2021 includes four phases of intervention: development or identification of the intervention, feasibility, evaluation, and implementation (Skivington et al., 2021). The students are randomized into three groups, intervention 1 (MR group), intervention 2 (video group), and control (Instructor-led) in a manner where the researcher has no influence on the allocation of the groups. Randomization is done using a computer program. The inclusion criteria are the following: the student is studying to become a nurse, student performing the NGT insertion procedure for the first time and had no theory or pre-material on the treatment procedure. Exclusion criteria include: the student has no previous nursing education (e.g. practice nurse), students have no epilepsy or the pacemaker.

In the second phase students answer questions about demographic information and answer a theoretical exam (pre-test) on nasogastric tube insertion to assess their baseline knowledge and skills. The pre-test is used to measure the homogeneity of the groups. Student performance is measured using a structured NGT checklist (primary endpoint). A structured NGT checklist are used to assess students' clinical competence and performance and based on a checklist to monitor how well students follow non-technical and technical procedural steps. (Kebede et. al 2024.)

After completion students answer the NGT theory post-test (secondary dependents). The usability of MR glasses and video is measured using The System Usability Scale (SUS) questionnaire (primary endpoint), secondary dependents are NASA's Task load index (TLX), User Experience Questionnaire (UEQ), and students' reflective text, where students describe their experiences with MR technology as teaching method and identify the factors that either facilitate or hinder the learning of nursing skills within an MR environment. The detailed description of the intervention:

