### Intervention group 1 (N=60):

- Mixed Reality Learning
- MR glasses technical training to students and teachers

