### Intervention group 2 (N=60):

- Video-Based Learning
- Video systems technical training to students and teachers

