### Control group (N=60):

- Instructor-led training
- Introduction of teachers to nasogastric tube insertion

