## Evaluation of intervention

Follow-up assessment after practice post-intervention (M1)

- System Usability Scale (SUS), User Experience Questionnaire (UEQ), NASA Task Load Index, NGT theory post-test
  - students answer after performance
  - Students reflection text (only MR group)
- Students move to another room and perform the NGT procedure without instruction.
  - A structured NGT checklist → assessed by research assistant or staff

Follow-up assessment six-month post-intervention (M2)

- Students perform NGT insertion again without instruction.
- A structured NGT checklist → assessed by research assistant or staff

Figure 1. intervention description

The sample size calculation is based on previous research by Schoeb et al., 2020. The calculation employs a delta value of 1,53 points, a standard deviation (SD) of 0,15 points, a type 1 error of 0.05, and a study power of 80%. The calculated sample size is 3 x 55 students, and the planned sample size is 3 x 60 students, based also on the Spring 2025 pilot, to account for potential attrition. A pilot data collection will take place in spring 2025, and the full data collection will occur from autumn 2025 to spring 2027. The detailed implementation of the study is described in the table below:

Paper I: Assess and comparing the learning outcomes of nursing students in NGT insertion using Mixed Reality Learning, Video-Based Learning and Instructor-led training - a research protocol for a randomized trial.
 
The research question: What kind of learning outcomes can be observed in nursing students in NGT insertion using Mixed Reality Learning, Video-Based Learning and Instructor-led training?
 
Article I: Assessing and comparing Mixed Reality Learning, Video-Based Learning and Instructor-led training in the context of performance in nasogastric tube insertion for nursing students: A randomized controlled study. Submission for autumn 2027.
			

Paper II: To assess and compare the MR technology and video usability.
 
Research question: How students experienced the usability of MR technology and video tools in learning how to insert a nasogastric tube.
 
Article II: Usability of MR and video technology in learning nursing skills in nursing education. Submission for spring 2027.
			

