First year nursing students (N=180).	Students practice NGT insertion into mannikin. The instructional material for all groups is the same included content from a technical and non-technical point of view. The only difference between the groups is the technology used to implement it.	
Students answer the questions (M0) about demographic information (students age, gender, educational background) and make NGT theory pre-test.
 
Students' clinical competence and performance assessed using an NGT checklist (primary endpoint). After the NGT was inserted, students answer NGT theory post-test (secondary dependent variable) and answer the questionnaires: System Usability Scale (SUS), User Experience Questionnaire (UEQ) and NASA Task Load Index. The SUS scale is five-point Likert scale (10 questions) and aims to determine which device, glasses or video was easier, more enjoyable, and more effective to use. Higher scores indicate better usability.
 
User Experience Questionnaire (UEQ) scales of the questionnaire cover a comprehensive impression of user experience. Both classical usability aspects (efficiency, perspicuity, dependability) and user experience aspects (originality, stimulation) are measured.
 
NASA Task Load Index (TLX) assesses workload on five 6-point scales, and it evaluates the mental workload and experiences of students while performing the task.
 
Students who use MR glasses send a written reflection after completing the procedure. Student experiences with MR glasses will be collected using a reflective learning journal rubric adapted from the model by Liu, Kitto & Shum (2021). Reflection text
	
Statistical analyses are performed using SPSS- software. Anova is used to compare the mean scores of the three groups on the total checklist scores and to assess which learning and teaching method influences students' NGT insertion learning outcomes. The P-value will be used to test whether the differences between the teaching methods are statistically significant. SUS and NASA TLX are analyzed with SPSS. Both video and glasses are given SUS and NASA TLX scores between 0-100. The value represents the level of usability and task workload. The results are analyzed with a T-test, which is a common method for comparing the means of two groups.
 
Student reflective analysis is an inductive approach using traditional content analysis of student written reports. Analyzed and coded using the software ATLAS.fi.
 
Statistical analysis will be ready spring 2027.

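### Allocation is not stated to be balanced within student intake and the stated tests carry no intake term: valid as written, but a cheap gain in balance and precision is left unused

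*Protocol*

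**What the plan says.** On allocation, section 3 (Research implementation) says that students are randomised to three groups "in a manner where the researcher has no influence on the allocation of the groups" and that "Randomization is done using a computer program". The box on baseline assessment adds only the names of the three groups. No ratio, block size or stratification factor is given.

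On size, each of the three arm headings in Figure 1 carries N=60, and the sample size paragraph says: "The calculated sample size is 3 x 55 students, and the planned sample size is 3 x 60 students". The gap between 55 and 60 is described as an allowance for attrition.

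On timing, the same paragraph says that "the full data collection will occur from autumn 2025 to spring 2027". The checklist is scored after practice (M1) and again six months later (M2).

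On analysis, Figure 2 says: "Anova is used to compare the mean scores of the three groups on the total checklist scores". The SUS and NASA TLX scores for glasses and video are compared with a t-test. No intake or semester term appears in either.

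**The concern.** The protocol sets a target of equal arms but states no rule that would produce them. It also sets a collection window long enough to need more than one intake of first-year students. Intakes can differ in cohort, in staff familiarity with the glasses and in who scores the checklist, since scoring may be done by a research assistant or by staff.

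Two things are at stake, both modest. If the program makes independent draws, the five-student margin meant for attrition can be used up by chance imbalance before anyone leaves. And if intakes differ in mean score, that variation stays in the residual of every comparison, although the factor is known without cost at enrolment.

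**Working it through.** **1. The plan's own figure.** Inputs from the sample size paragraph: delta 1.53, SD 0.15, alpha 0.05, power 80%.

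- Standardised difference: 1.53 / 0.15 = 10.2.
- Normal approximation, two-sided: n = 2 × (1.960 + 0.842)² / 10.2² = 15.70 / 104.04 = 0.15, so 1 per arm. By three-group ANOVA, 2 per arm already gives over 99% power.

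The stated 55 per arm is therefore not reproduced. That is a separate problem. To give power a scale here, I invert the calculation: 55 per arm with 80% power (two-sided t-test, alpha 0.05) corresponds to d = 0.539, or an SD of about 1.53 / 0.539 = 2.84. For the overall ANOVA it corresponds to f = 0.244. Both are working assumptions, not figures from the protocol.

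**2. How many intakes.** A single autumn 2025 intake would complete M2 around spring 2026. An M2 ending in spring 2027 puts the last M1 sessions around autumn 2026. So there are at least two intakes, and up to three (autumn 2025, spring 2026, autumn 2026). This is inferred from the dates; the protocol does not state it.

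**3. Arm sizes, if allocation is unrestricted 1:1:1 over 180 students.**

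- SD of an arm size: √(180 × 1/3 × 2/3) = √40 = 6.3.
- 95% range: 60 ± 1.96 × 6.32, about 48 to 72.
- From 1,000,000 simulated allocations: exactly 60/60/60 in 0.5%, smallest arm below 55 in 55%, smallest arm below 50 in 14%, median smallest arm 54.

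**4. What that imbalance costs** (d = 0.539 for pairs, f = 0.244 for ANOVA).

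| Arms | ANOVA power | Pairwise power, smallest v middle arm |
|---|---|---|
| 60/60/60 | 83.6% | 83.4% |
| 54/60/66 | 83.3% | 81.3% |
| 48/60/72 | 82.5% | 78.8% |

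Averaged over unrestricted allocations, pairwise power is 83.0%, against 83.4% with equal arms: a loss of about 0.4 points.

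**5. What an intake term gains.** If intake explains a share r of the outcome variance, adjustment turns d into d / √(1 − r). The protocol gives no value for r, so a range is shown, at 60 v 60.

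| r (assumed) | Adjusted d | Pairwise power |
|---|---|---|
| 0 | 0.539 | 83.4% |
| 2% | 0.545 | 84.1% |
| 5% | 0.553 | 85.2% |
| 10% | 0.568 | 87.0% |

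**6. Why the two changes belong together.** With allocation balanced within three equal intakes but an unadjusted ANOVA, simulated type I error at nominal 5% is 4.3% for r = 5% and 3.5% for r = 10%. Stratifying without adjusting makes the test conservative.

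**The case against.** The strongest reply is that simple computer randomisation followed by an unadjusted ANOVA is a valid analysis, that the protocol is merely silent, and that model covariates are commonly left to a statistical analysis plan, which is not at hand. Most of this stands, and it rules out several stronger readings.

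- *That allocation is unrestricted and the arms will be unequal.* A computer program can equally run a blocked list, and the N=60 on each arm may point that way. The 55% figure is conditional. Moreover, 55 does not follow from the stated inputs, so falling below it is not a meaningful loss in itself; the power figures above are the better measure.
- *That intake confounds the method effect.* Chance imbalance in intake mix is random error, not bias, and the ANOVA error term already reflects it.
- *That the intake effect is large.* Shifts of 0.3 to 0.5 SD between three equal intakes would make intake 5.7% to 14.3% of the variance. Even then the standard error of an arm difference rises only from √(2/60) = 0.183 to 0.188-0.197 SD. Nothing in the documents supports those shifts. One university, the same instructional content, a structured checklist and teacher preparation all argue for smaller ones.
- *That an intake factor removes the effect of growing staff experience with the glasses.* That experience bears on the MR arm alone, so it is an arm-by-intake interaction. An additive factor leaves it in place, averaged over intakes.

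What the reply does not meet is that the allocation method has to be settled before students are allocated and cannot be supplied later by an analysis plan.

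**Conclusion.** The point holds as a design improvement, not as an error that invalidates the trial. The protocol plans equal arms without stating a rule that secures them, and the analyses it names leave any intake variance in the residual. If allocation is unrestricted, the cost is on average under 1 point of power. Omitting intake forgoes about 1 to 4 points if intake explains 2-10% of the variance. Both sizes rest on the assumed d = 0.539, and the second also on an assumed variance share. More than one intake is an inference from the dates. A reader might infer bias, or a trial that will miss its required numbers; the documents support neither. Priority is low to moderate: the gain is modest, but so is the cost.

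**What to change.** In section 3, next to the sentence on the computer program, state the ratio as 1:1:1 and specify permuted blocks of concealed, varying size, generated separately for each intake (semester). If the program already works this way, one sentence settles this half.

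In the Analysis column of Figure 2, add intake as a fixed factor to the checklist ANOVA and to the SUS and NASA TLX comparison, which then becomes a two-factor model rather than a plain t-test.

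Make both changes together. If recruitment has begun, apply the blocking from the next intake and include the factor for all students.

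The cost is one setting in the randomisation program, one model term, and one or two degrees of freedom (two or three intakes). No extra students are needed. The factor will not remove a learning curve specific to the MR arm.

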## Students baseline assessment (M0):

- Demographic information (students age, gender, education and use of previous device background)
- NGT theory pre-test
- Inclusion and exclusion criteria

Randomization according to intervention 1 (MR) group, intervention 2 (video) group and control (instructor) group

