
	
consisting open-ended questions in which students describe their learning process in their own words.
 
After six -month (M2) students perform NGT insertion again without instruction. Performance assessed NGT checklist.
	
--	---	--

Figure 2. implementation of the study

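### The theory pre-test is given only a homogeneity role and checklist totals go to an ANOVA with no covariate: valid, but a small missed efficiency that a prespecified ANCOVA would recover at almost no cost

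*Protocol*

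**What the plan says.** Section 3 (Research implementation) says that students sit a theory exam before training to assess baseline knowledge and skills, and then: "The pre-test is used to measure the homogeneity of the groups". It states no other use for the score.

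The Analysis column of Figure 2 gives the checklist comparison: "Anova is used to compare the mean scores of the three groups on the total checklist scores". It names no covariate, and the protocol nowhere mentions ANCOVA or adjustment.

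The checklist, a primary endpoint, is scored twice. At M1, "Students move to another room and perform the NGT procedure without instruction". For M2, Figure 2 says: "After six -month (M2) students perform NGT insertion again without instruction". The theory post-test is a secondary variable with no stated analysis.

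On timing, the baseline list (M0) contains "NGT theory pre-test", and below that list comes "Randomization according to intervention 1 (MR) group, intervention 2 (video) group and control (instructor) group". The narrative in section 3 runs the other way: it describes randomisation first and then introduces the pre-test as part of the second phase.

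The inclusion criteria require that students "had no theory or pre-material on the treatment procedure".

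**The concern.** A homogeneity check of randomised arms can show only chance differences, and the protocol attaches no consequence to finding one. The same score, entered as a covariate, would correct the arm comparison for whatever chance difference arises and would remove the part of the outcome variance that it explains. As written, an analyst would describe the pre-test by arm and then leave it out of the comparison.

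What is at stake is precision, and some protection against a later decision to adjust made after the imbalance has been seen. Bias is not at stake.

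**Working it through.** **Inputs.** Three arms, with 3 x 60 planned and 3 x 55 calculated (protocol, sample size paragraph under Evaluation of intervention). The pre-test/outcome correlation r is not in the protocol, so it is varied from 0 to 0.5; it may differ between M1 and M2. The protocol gives no precision figure to reproduce here. Its delta, SD and power do not enter, so the results do not depend on how 3 x 55 was reached.

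**Formula.** Let N be the total number of students, n the number per arm and k = 3 arms. With a normally distributed covariate, the expected variance of a pairwise adjusted difference, relative to the unadjusted one, is

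factor = (1 - r²) x (1 + 1/(N - k - 2)) = (1 - r²) x (1 + 1/(N - 5)).

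The first term is the variance explained. The second is the cost of estimating the slope.

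**Break-even.** Setting the factor to 1 gives r = 1/√(N - 4):
- N = 180: 1/√176 = 0.075
- N = 165: 1/√161 = 0.079

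**Results.** The 95% CI half-width, in outcome SD units, is t(0.975, df) x √((2/n) x factor). Unadjusted, the factor is 1 and the half-width is 0.3603 at 3 x 60 (df 177) and 0.3766 at 3 x 55 (df 162). Adjusted, df is 176 and 161.

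| r (assumed) | Factor, 3 x 60 | Change in variance | Half-width | Factor, 3 x 55 | Half-width |
|---|---|---|---|---|---|
| 0 | 1.0057 | +0.6% | 0.3613 | 1.0063 | 0.3778 |
| 0.1 | 0.9957 | -0.4% | 0.3595 | 0.9962 | 0.3759 |
| 0.2 | 0.9655 | -3.5% | 0.3540 | 0.9660 | 0.3701 |
| 0.3 | 0.9152 | -8.5% | 0.3447 | 0.9157 | 0.3604 |
| 0.5 | 0.7543 | -24.6% | 0.3129 | 0.7547 | 0.3271 |

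Worked line, r = 0.3 at 3 x 60: (1 - 0.09) x (1 + 1/175) = 0.91 x 1.0057 = 0.9152.

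**Check.** A simulation of 20,000 trials per value of r at 3 x 60 gave variance ratios of 1.004 (r = 0), 0.997 (0.1), 0.917 (0.3) and 0.755 (0.5), in line with the formula.

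**Where r may lie.** Eligible students have had no NGT theory, so pre-test scores could sit near the floor. A floor narrows the spread of the pre-test and would weaken its correlation with both outcomes. The checklist is also a practical score, one step further from a written exam than the theory post-test is.

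**The case against.** The strongest objection is that nothing here is wrong. The ANOVA is valid, the gain on the one analysis that the protocol states is probably slight, and a statistical analysis plan that is not shown could add covariates. At r = 0.2 the half-width moves only from 0.3603 to 0.3540 SD, which would rarely change a conclusion. The larger gains belong mainly to the theory post-test, for which no analysis is stated.

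Most of this stands, and it sets the weight of the point. It does not remove the point, because the protocol does more than stay silent: it names the test for a primary endpoint and assigns the pre-test a role. The change proposed is to that stated choice. The lack of an analysis for the post-test is not a complaint here.

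Three stronger readings should be resisted.
- A reader might infer that the unadjusted comparison is biased. Randomisation rules that out.
- A reader might take a break-even of about 0.08 as a promise of benefit on the checklist. At break-even the gain is nil.
- A reader might count on a gain of 8.5% to 24.6% for the post-test. That needs r of 0.3 to 0.5, which the protocol does not support with any figure and which a floor effect could prevent.

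The timing is also less settled than the M0 list suggests. The narrative in section 3 puts randomisation before the pre-test, so the score is a clean baseline covariate only once the order is confirmed.

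**Conclusion.** The point holds as a small missed efficiency, for consideration only. The stated ANOVA is valid and unbiased. At 3 x 60, adjustment changes the variance of a pairwise difference by between +0.6% (r = 0) and -24.6% (r = 0.5). The gain on the checklist is probably small. A useful gain needs r of about 0.3 or more, which is more plausible for the theory post-test.

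This rests on an assumed range for r, a roughly linear relation between pre-test and outcome, and a pre-test taken before allocation. The case for change is the asymmetry: little can be lost, and the score is to be collected anyway.

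**What to change.** In section 3 and the Analysis column of Figure 2, replace the ANOVA of checklist totals at M1 and at M2 with a prespecified ANCOVA, with arm as factor and NGT theory pre-test score as covariate, applied whatever imbalance is observed. If the arms are compared on the theory post-test, use the same model there. The descriptive homogeneity check can stay.

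Reconcile the narrative in section 3 with the M0 list so that both state that the pre-test is completed before allocation.

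Cost: a sentence or two of wording, and one residual degree of freedom (177 to 176 with 180 students, 162 to 161 with 165). The expected variance rises by at most 0.6% if the pre-test proves uninformative. No new data are needed, and SPSS, the named software, fits the model. The change should be fixed before outcome data are analysed.
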